1. INTRODUCTION

1.1. Indication

PF-06293620 (RN909) is a glucagon receptor antagonist being developed for the treatment of type 2 diabetes mellitus (T2DM).

[figure not shown]
1.2. Background

Type 2 diabetes mellitus (T2DM) is a metabolic disorder afflicting over 25 million Americans and is growing rapidly in prevalence. Hyperglycemia is the primary clinical characteristic of T2DM, and is attributed to an underlying pathophysiology of insulin resistance, excess hepatic glucose production and deficient insulin production. Longstanding T2DM can lead to macro- and microvascular disease, resulting in a variety of complications, the most prevalent being cardiovascular disease, nephropathy, retinopathy and neuropathy. A number of large clinical outcome trials have demonstrated that improved glycemic control is associated with decreased microvascular complications ([Patel](#); [Turner](#)).

In addition to insulin, glucagon is a major hormone maintaining moment-to-moment glucose homeostasis. Glucagon counteracts glucose-lowering by insulin via the promotion of hepatic glucose production, thereby maintaining euglycemia and protecting against hypoglycemia. There is a growing appreciation for the potential role of glucagon in contributing to hyperglycemia in T2DM stemming from the observation that glucagon levels are inappropriately elevated in the T2DM hyperglycemic milieu ([Ali](#); [Dunning](#)). Therefore, mitigating the effects of hyperglucagonemia in T2DM is an attractive approach for treating hyperglycemia.

PF-06293620 is a humanized IgG2 Δ a monoclonal antibody that binds to, and blocks glucagon signaling through, the human glucagon receptor. Glucagon binding activates glucagon receptors found primarily on hepatocytes, leading to increased hepatic glucose production by a number of mechanisms including increased gluconeogenesis and glycogenolysis. PF-06293620 ameliorates elevations in plasma glucose, which are in part mediated by hyperglucagonemia, through normalization of dysregulated hepatic glucose production. Furthermore, as this mechanism is not dependent on functional pancreatic beta cells, it is anticipated to have a durable effect of improved glycemic control in subjects with T2DM.

CCI

PF-06293620

[figure not shown]
B3501001

Final Protocol Amendment 3 02 October 2015

CCI

CC1

1.3. Rationale

1.3.1. Study Rationale

The first-in-human study is a randomized, double-blinded (Sponsor-open), placebo-controlled, single ascending-dose (SAD) and multiple ascending-dose (MAD) study in subjects with T2DM on a stable regimen of metformin. This population was chosen because it is the target population for this investigational drug and the preclinical studies support its safety for initiating clinical trials in medically-stable T2DM subjects.

Furthermore, studying this population affords the opportunity to obtain an earlier assessment of this investigational drug's pharmacodynamic activities, allowing for dose selection in future studies. Plasma glucagon and GLP-1 levels will be used as biomarkers to assess pharmacodynamics related to target modulation. A number of glycemic parameters will be used to assess pharmacodynamics related to glycemic control: fasting plasma glucose (FPG), postprandial glycemia (during mixed meal tolerance test [MMTT]), 24 hour glucose AUC and weighted mean daily glucose (from fingerstick assessment), 1,5-anhydroglucitol, fructosamine and HbA1c. In conjunction with some of these tests (eg, MMTT), insulin and C-peptide levels will also be measured to gain additional insights into PF-06293620 effects on glucose homeostasis.

To fully characterize the safety profile, the investigational drug will be administered subcutaneously (SC) and intravenously (IV) in the SAD cohorts. PF-06293620 will be dosed in an ascending fashion with staggered dosing starts within each cohort to ensure adequate clinical safety has been ascertained before proceeding with the remainder of the subjects within the cohort. In addition, data collected for each SAD cohort will be reviewed when at least 8 subjects have completed Day 15 assessments before proceeding to the next higher dosage level.

Based on a review of the preliminary, unpublished safety, pharmacokinetic (PK) and PD results from the first four SAD dose cohorts, a randomized, double-blind (Sponsor open), placebo-controlled, multiple ascending dose (MAD) portion will be initiated to evaluate the safety and tolerability of ascending multiple dosages and dosing-schedules. The MAD cohorts will run in parallel with the remaining SAD cohorts. Based on the ongoing review of

the safety data of the previous SAD and MAD cohort(s) the order of initiation of the MAD cohorts may be adjusted. MAD safety data from the previous cohort(s) will be used to determine the dose and dose regimen of the fourth planned cohort. At no time will the MAD dose exceed the PK exposure from the SAD. An additional fifth cohort may be studied to obtain further safety and PK data, increasing the planned total number of subjects to approximately 50. For MAD dose escalation, the decision to proceed to the next dose will be made by the Pfizer study team and the Investigators after review of the available safety and tolerability data after 80% of the subjects in the previous cohort have received one dose and have been followed for 14 days post first dose. Enrollment in the previous cohort must be completed before initiating enrollment in a new cohort.

1.3.2. Preliminary Unpublished Data (blinded)

Subject Disposition and Baseline Characteristics (data-cutoff May 19, 2015)

Thirty-six subjects have been randomized, of which 12 have completed the study. To date, three subjects have discontinued from the study. One subject in Cohort 4 was no longer willing to participate and discontinued on Day 8; this subject was replaced with another subject. Two other subjects were no longer willing to participate in the study and were terminated early (1 each in the 1.0 mg/kg cohort and the 3.0 mg/kg cohort) and were not replaced.

The baseline characteristics of the subjects randomized to date in the SAD study are summarized in Table 1 below.

Table 1. Baseline Characteristics – SAD Cohorts, Study B3501001

Characteristics	Placebo N=9	Cohort 1 (0.3 mg/kg) N=6	Cohort 2 (1.0 mg/kg) N=6	Cohort 3 (3.0 mg/kg) N=6	Cohort 4 (6.0 mg/kg) N=9
Age ^{1,2}	57.1 ± 6.5	60.7 ± 4.5	60.7 ± 6.2	57.7 ± 4.5	57.4 ± 8.7
Gender ² (M:F)	4:5	5:1	2:4	3:3	5:4
Weight ^{1,2} (kg)	89 ± 21	93 ± 9	77 ± 14	90 ± 11	88 ± 16
BMI ^{1,2} (kg/m ²)	31.0 ± 4.6	32.3 ± 3.7	29.1 ± 3.3	30.8 ± 3.2	32.1 ± 3.4
Duration T2DM ³ (years)	10.9	13.4	10.0	8.5	8.1
Baseline HbA1c ^{1,4} (%)	8.7 ± 1.0	8.1 ± 0.9	7.7 ± 0.6	8.2 ± 0.5	8.3 ± 0.7

¹ Mean ± SD; Source; ² Table 14.1.2.1 (B3501001 IND Tables); ³ Table 14.1.2.2 (B3501001 IND Tables);

⁴ Table 14.4.7.5.1 (B3501001 IND Tables).

Pharmacokinetics (data-cutoff May 19, 2015)

As of May 19th 2015, preliminary, unpublished PK of PF-06293620 are available from the first 4 cohorts (0.3, 1, 3, and 6 mg/kg) in the ongoing single ascending dose study in subjects with T2DM. Following administration of single subcutaneous doses of PF-06293620, absorption was slow with median C_{max} occurring approximately 4-10 days post dose. After that the decline in concentration was slow and multiphasic with mean terminal half-life (t_{1/2}) ranging from 9 to 18 days as the doses increased from 0.3 to 3 mg/kg. Both C_{max} and total

exposure (AUC_{inf}) increased slightly greater than dose proportionally with increasing doses up to 6 mg/kg. Table 2 below summarizes the PF-06293620 preliminary, unpublished PK parameters.

Table 2. Geometric Mean (%CV) Plasma PF-06293620 Pharmacokinetic Parameter Values, Study B3501001 (Preliminary, unpublished, based on QCed data)

Parameter	PF-06293620 Treatment			
	0.3 mg/kg SC	1 mg/kg SC	3 mg/kg SC	6 mg/kg SC
N, n	6,2	6,5	6,6	6,0
AUC _{inf} (µg·hr/mL)	260	1748 (46)	6606 (45)	NC

1.3.3. Dose Rationale

The initial starting dose was selected based upon the results from preclinical pharmacological, PK and toxicology studies as well as PK/PD modeling and simulation. The maximum recommended human starting dose (MRSD) was determined based on the "no-observed-adverse-effect-level" (NOAEL) in the pivotal, 3-month, monkey toxicology study. Proposed doses, along with anticipated safety margins are listed in Table 3 below.

Table 3. Proposed PF-06293620 SAD Doses and Predicted Safety Margins based on the Exposures in Monkeys

Proposed PF-06293620 FIH Dose (mg/kg)	Route	Predicted PF-06293620 Human Exposure		Projected Safety Margin* (fold)	
		C _{max} (µg/mL)	AUC _{inf} (µg*hr/mL)	C _{max}	AUC
0.3	SC	3.16	1144	620	162
1	SC	10.5	3812	187	49
3	SC	31.6	11435	62	16
6	SC	63.2	22870	31	8
1	IV	38.5	7059	314	89

Exposure at NOAEL doses (200 mg/kg) in monkeys:
 IV: C_{max} = 12,100 µg/mL; AUC = 625,000 µg*hr/mL
 SC: C_{max} = 1,960 µg/mL; AUC = 185,000 µg*hr/mL
 *Margin calculated based on the NOAEL exposure/predicted human exposure
 Source: Table 2.5-2 (Clinical Overview)

The proposed starting dose of 0.3 mg/kg SC represents a 667-fold lower dose than the NOAEL dose of 200 mg/kg (SC) in the pivotal, 3-month, toxicity study. Furthermore, the starting dose is approximately 3-fold less than the minimum efficacious dose of 1 mg/kg in monkey and is expected to show no to minimal pharmacological response in humans. The predicted maximal PF-06293620 concentration (C_{max}) of 3.16 µg/mL is 620-fold lower than the observed C_{max} and the predicted AUC of 1144 µg·h/mL is 162-fold lower than the observed AUC at the NOAEL dose of 200 mg/kg (SC) in the 3-month toxicity study in monkeys. The maximum dose proposed for this study is 10 mg/kg IV. The predicted human C_{max} and AUC at the highest proposed dose would be approximately 31- and 9-fold below the maximum observed exposures at 200 mg/kg (IV) in monkey in the pivotal, 3-month, toxicity study, respectively. The dosage range encompasses the theoretical efficacious dose. However, based on preliminary, unpublished PD results in subjects receiving single ascending doses up to 6 mg/kg SC, maximal (nadir) decrease in FPG appeared to plateau by 3 mg/kg and no additional FPG lowering is expected at 10 mg/kg IV. Therefore, it is not necessary to test the highest dose, 10 mg/kg IV, initially proposed in the study and hence has been removed in the current amendment.

MAD

The proposed PF-06293620 doses in the MAD portion were selected based on the preliminary PK/PD analysis and simulation from available data from the first 4 cohorts in the ongoing SAD study. Fixed dosages of 75, 150 and 250 mg Q4W were selected for this study to allow for adequate characterization of both the dose-response relationship for glycemic analytes (FPG, MMTT, mean daily glucose [MDG] and HbA1C), as well as to identify the maximum tolerated dose. Modeling suggests minimal accumulation ($R_{ac}=1.14$) of PF-06293620 after 3 dosages at 75 mg Q4W and approximately 1.4 and 1.6-fold increase in the exposure is predicted at 150 and 250 mg Q4W dosages, respectively. However, the predicted exposure at the highest dose (250 mg Q4W, ~3.1 mg/kg) is not expected to exceed the observed exposure at 6 mg/kg single-dose. The 6 mg/kg dose was found to be safe and well-tolerated. Guided by the dose-response relationship for baseline-adjusted FPG, the doses of 75 mg, 150 mg and 250 mg Q4W are deemed appropriate and adequate to allow for characterization of the dose-response relationship for PK, and PD changes. The 250 mg dose is expected to result in maximal fasting plasma glucose lowering. The 75 mg Q4W would approximately represent the dose for 50% maximal effect (ED50) and an intermediate dose of 150 mg Q4W was also proposed.

Proposed MAD doses, along with anticipated safety margins are listed in Table 4 below. The predicted human C_{max} and AUC_{tau} at the highest proposed dose would be approximately 122- and 20-fold below, respectively, the maximum observed exposures at 200 mg/kg (SC) in monkey in the pivotal, 3-month, toxicity study.

Table 4. Proposed PF-06293620 MAD Doses and Predicted Safety Margins based on the Exposures in Monkeys

Proposed PF-06293620 MAD Doses (mg)	Regimen	Predicted PF-06293620 Human Exposure		Projected Safety Margin*(fold)	
		C_{max} (μ g/mL)	AUC_{tau} (μ g*hr/mL)	C_{max}	AUC
75	Q4W	3.0	1471	653	126
150	Q4W	8.0	4486	245	41
250	Q4W	16.1	9448	122	20
TBD	TBD	--	--	--	--

Exposure at NOAEL doses (200 mg/kg) in monkeys:

IV: $C_{max} = 12,100 \mu$ g/mL; $AUC = 625,000 \mu$ g*hr/mL

SC: $C_{max} = 1,960 \mu$ g/mL; $AUC = 185,000 \mu$ g*hr/mL

*Margin calculated based on the NOAEL exposure/predicted human exposure

Source: Supportive Table 6 (RN909 Study B3501001: Preliminary PK report, May 2015)

2. STUDY OBJECTIVES AND ENDPOINTS

2.1. Objectives

2.1.1. Primary Objective

- To evaluate the safety, tolerability and immunogenicity of single, ascending SC and IV doses and ascending multiple SC doses of PF-06293620 in subjects with T2DM on stable doses of metformin.

2.1.2. Secondary Objectives

- To characterize the pharmacokinetics of PF-06293620 after administration of single-doses of SC and IV PF-06293620 and multiple doses of SC PF-06293620 to subjects with T2DM on stable doses of metformin.

2.1.3. Exploratory Objectives

- To characterize the pharmacodynamics of PF-06293620.
- To characterize the effect of PF-06293620 on (post-prandial) glucose, insulin, GLP-1, C-peptide and glucagon excursions over 4 hrs following an MMTT.
- To evaluate changes in fasting lipid parameters.
- Additional exploratory objectives in the MAD portion will include 24 hour ambulatory blood pressure monitoring, and central review of ECGs .

2.2. Endpoints

2.2.1. Primary Endpoints

- Incidence of dose limiting or intolerable treatment related adverse events (AEs).
- Incidence, severity and causal relationship of treatment emergent AEs (TEAEs).
- Incidence of anti-drug-antibodies.

2.2.2. Secondary Endpoints

- Single- and multiple-dose pharmacokinetic parameter estimates of PF-06293620 include: C_{max} , C_{av} , C_{min} , T_{max} , CL or CL/F , V_{ss} or V_z/F , half-life, AUC_{last} , AUC_{τ} , R_{ac} and AUC_{inf} as the data permit and as appropriate for SAD and MAD cohorts.

2.2.3. Exploratory Endpoints

- Change in pharmacodynamic parameters, including FPG, glucagon, GLP-1, 1,5-anhydroglucitol, fructosamine, HbA1c, AUC_{0-24hr} of blood glucose and mean daily blood glucose levels (from fingerstick).

- Post-prandial PD endpoints including glucose, glucagon, insulin, GLP-1 and C-peptide excursions defined as AUC₀₋₄ (change from baseline) in response to MMTT.
- 24-hour glucose AUC and weighted mean daily glucose.
- Lipid parameters (change from baseline) including: triglycerides, total cholesterol, HDL-C, and LDL-C.
- 24 hour ambulatory blood pressure monitoring, and central review of ECGs (MAD Cohorts only).

3. STUDY DESIGN

3.1. Study Overview

This is a randomized, placebo-controlled, double-blind (sponsor unblinded; subjects and Investigator blinded), single dose, and multiple-dose dose escalation study of PF-06293620. The study was originally to be conducted in approximately 6 planned single-dose cohorts. Based on the preliminary, unpublished, results from the first 4 SAD cohorts, the 1 mg/kg IV cohort will be evaluated but the 10 mg/kg IV cohort will not be conducted. Approximately 4 multiple dose cohorts are planned in an effort to seek a maximum tolerated dose (MTD) and evaluate different dosages for safety and tolerability. The multiple-dose cohorts will be initiated based on a review of the preliminary, unpublished safety and PK results from the first three SAD dose cohorts. The planned dosages, the route of administration, frequency of administration and the approximate number of subjects for the SAD cohorts are shown in [Table 5](#) and for the MAD cohorts in [Table 6](#) below.

Single-Dose Cohorts:

The SAD portion will be conducted in approximately 5 planned cohorts (a 6:2 ratio of active drug to placebo) with a total of up to approximately 40 subjects in an effort to seek a maximum tolerated dose (MTD). PF-06293620 will be administered subcutaneously(SC) at doses of 0.3, 1, 3, and 6 mg/kg. In addition, a 1 mg/kg dose, will be given intravenously (IV). The screening period will last up to 28 days and the treatment period will last approximately 84 days. Subjects will be required to be on stable, daily dosages of metformin. Subjects will receive a single dose of study treatment (PF-06293620 or placebo) on Day 1, with multiple PK and safety assessments during the confinement period in Clinical Research Unit (CRU) on study Days -1, 1, 2, 3 and 4 and will be discharged on Day 5. The subjects will return to the CRU for subsequent visits at which time safety assessments, including AE monitoring, clinical laboratory tests, vital signs, and ECG, as well as PK, MMTT, lipid and PD biomarker labs will be performed (See [Schedule of Activities](#)- SAD). In each SAD cohort, the first 2 subjects will be dosed with either PF-06293620 or placebo and observed for 24 hours. If no acute toxicity is observed in the first 24 hours, as defined in [Section 3.3.1](#), the remaining subjects in the cohort will proceed with dosing of either PF-06293620 or placebo. Dose escalation will not occur until all subjects in the cohort are enrolled and at least 6 subjects in

the cohort reach Day 15 post-dose, and the safety data have been thoroughly reviewed by the Sponsor and Investigators.

Table 5. Anticipated Number of Cohorts and Dosage Levels

Cohort	RN909 Dose	Route	Number of Subjects
1	0.3 mg/kg	SC	6
	Placebo		2
2	1 mg/kg	SC	6
	Placebo		2
3	3 mg/kg	SC	6
	Placebo		2
4	6 mg/kg	SC	6
	Placebo		2
5	1 mg/kg	IV	6
	Placebo		2

Multiple-Dose Cohorts

Based on a review of the preliminary, unpublished safety, PK and PD results from the first four SAD dose cohorts, a randomized, double-blinded (Sponsor-open), placebo-controlled, multiple ascending dose (MAD) portion will be initiated to evaluate the safety and tolerability of different dosages and dosing schedules. This portion will be conducted in approximately 4 planned cohorts, 75 mg, 150 mg, 250 mg, and a fourth cohort with dosage and regimen to be determined based on the review of the safety data from the previous cohort(s), with a total of up to approximately 40 subjects (8 PF-06293620: 2 placebo per cohort). Subjects and the site personnel in the MAD cohorts will be blinded to treatment and treatment regimen. The MAD cohorts will be run in parallel with the remaining SAD cohorts. Based on the ongoing review of the safety data of the previous SAD and MAD cohort(s) the order of initiation of the MAD cohorts may be adjusted. MAD safety data from the previous cohort(s) will be used to determine the dose and dose regimen of the fourth planned cohort. An additional fifth cohort may be studied to obtain further safety and PK data, increasing the planned total number of subjects to approximately 50. At no time will the MAD dose exceed PK exposure from the SAD.

The MAD screening period will last up to 42 days, the treatment period will last 85 days the follow-up period will last approximately 85 days (Days 86-169). Subjects will be required to be on stable, daily dosages of metformin. Subjects will receive SC administration of study drug (PF-06293620 or placebo) every 4 weeks (on study Days 1, 29 and 57) in 3 of the currently planned 75 mg, 150 mg and 250 mg cohorts.

Subjects will be confined to the CRU prior to dosing (Day -3) for baseline testing, then will receive the first dose of study drug on Day 1. Subsequently, multiple PK and safety assessments after dosing will continue in the CRU until discharged on Day 3. The subjects will return to the CRU for subsequent visits at which time safety assessments, including AE monitoring, clinical laboratory tests, vital signs, and ECG, as well as PK, MMTT, lipid and PD biomarker labs will be performed (see [Schedule of Activities](#) - MAD). These visits will

include confinement for closer monitoring and PD testing (Days 6-8, 27-29, 62-64, and 83-85) with outpatient visits interspersed at regular intervals (generally Q2 weeks).

Table 6. Anticipated Number of MAD Cohorts and Dosage Levels

RN909 Dose	Route	Frequency	Number of Subjects
75 mg Placebo	SC	Q4 weeks	8 2
150 mg Placebo	SC	Q4 weeks	8 2
250 mg Placebo	SC	Q4 weeks	8 2
TBD Placebo	SC	TBD*	8 2

TBD: to be determined; *Dose frequency will be determined based on the review of the safety and PK data from the previous cohort(s). Frequency may range from Q2 weeks to Q8 weeks.

The order of MAD cohorts may be adjusted based on the safety of the previous cohort(s), but at no time will the dose exceed the PK exposure from the SAD portion. An additional cohort may be added to obtain additional safety and PK data.

3.2. Planned Number of Subjects

The overall planned number of subjects enrolled is approximately 80 subjects (approximately 40 subjects across the SAD cohorts and approximately 40 subjects across the MAD cohorts). [Table 2](#) and [Table 3](#), above, outline how the subjects will be distributed across the cohorts and treatments.

3.3. Dose Escalation and Stopping Rules

Dose escalation stopping rules will be used to determine whether the maximal tolerated dose has been attained. Dose escalation may be stopped if it is determined that the dose or dose regimen is deemed not to be tolerable. This decision will be made after a discussion takes place between the Pfizer study team and the investigator(s). The Pfizer study team may not overrule the Investigators' decision to stop dose escalation. If dose escalation is stopped due to any of these findings, additional cohorts may receive the same or lower doses of the investigational compound. Additional subjects may be added at a dose level to further evaluate safety and/or tolerability after discussions between the Pfizer study team and the investigators.

Single Ascending Dose Portion (n=8; 6 active treatment and 2 placebo)

Dose escalation will be terminated based on the following criteria:

- Two or more subjects receiving PF-06293620 drug (but not placebo subjects) develop similar clinically significant laboratory, ECG or vital signs abnormalities, or severe AEs in the same organ class, indicating dose-limiting toxicity as outlined in

Table 3 (Exception: dose escalation will be terminated if one (1) subject experiences ≥ 2 hypoglycemic events of Common Terminology Criteria for Adverse Events (CTCAE) Grade ≥ 3 which do not meet SAE criteria; see [Table 7](#)).

- It is determined that the dose is deemed intolerable. This decision will be made following discussions between the Study Team and the Investigator.

Other findings that, at the discretion of the Study Team and Investigator, indicate that dose escalation should be halted.

In the single dose cohorts, for any treatment-related serious adverse event (SAE), the subject will continue with the safety assessments until completion of the study.

Progression to the next dose will occur if the last dose was well tolerated and after satisfactory review of the available safety data.

Multiple Ascending Dose Portion (n= 8 PF-06293620 drug :2 PBO)

For dose escalation, the decision to proceed to a higher dose will be made by the Pfizer study team and the Investigators after review of the available safety and tolerability data after 80% of the subjects in the previous cohort have received one dose and have been followed for 14 days post first dose. Enrollment in the previous cohort must be completed before initiating enrollment in a new cohort. If ≤ 2 subjects in a cohort discontinues the study prior to reaching Day 15, for reasons other than safety (eg, withdraw of consent), the subject(s) will be included in the dose escalation data review and do/does not need to be replaced for the purposes of determining dose escalation. The order of MAD regimen cohorts may change depending on the ongoing review of safety/PK data but at no time will doses be administered that exceed the PK exposure determined in the SAD portion. Dose escalation will be terminated based on the following criteria:

- Two (2) or more subjects receiving PF-06293620 drug (but not placebo subjects) develop similar clinically significant laboratory, ECG or vital signs abnormalities, or severe AEs in the same organ class, indicating dose-limiting toxicity as outlined in [Table 3](#) (Exception: dose escalation will be terminated if one (1) subject experiences ≥ 2 hypoglycemic events of CTCAE Grade ≥ 3 which do not meet SAE criteria; see [Table 7](#)).
- The limit of safety and/or tolerability has been reached.
- If dose escalation in the single ascending dose is terminated AND the exposure of the dose cohort in the multiple ascending dose portion is equal to or higher than the exposure of the dose determined to be the MTD after the single doses.

Dose Interruption

- If ALT or AST are increased $\geq 3 \times$ ULN, ALT and AST will be monitored at least weekly. If ALT or AST continues to rise ≥ 3 to $\leq 5 \times$ ULN prior to the next dose, the investigator and Sponsor will review the subject's clinical data prior to administering the next dose and dosing may be interrupted.
- Dosing will be interrupted in individual subjects when the following occurs:
 - a. Serum AST or ALT are increased to $>5 \times$ ULN (CTCAE Grade ≥ 3); confirmed within 7 days (by both local and central labs).
 - b. Confirm creatine kinase (CK) WNL and source of enzyme elevation is not muscle related.

If ALT or AST elevation of $>5 \times$ ULN (CTCAE Grade ≥ 3) is confirmed, ALT and AST will be monitored weekly until liver enzymes have returned to WNL if subject was WNL at baseline; or to $<2 \times$ ULN if was between 1 – 2 \times ULN at baseline. Once ALT/AST levels have returned to WNL if subject was WNL at baseline; or to $<2 \times$ ULN if was between 1 – 2 \times ULN at baseline, the results must be confirmed within 7 days (by both local and central labs), at which point dosing may resume as scheduled per protocol. Missed doses will not be made up. If dosing is interrupted, all study visits and procedures will continue as per protocol, with the exception of dosing and subject will be followed to the end of the study.

If following the Day 1 dosing is interrupted due to ALT or AST elevation, the dosing windows for Day 29 or Day 57 may be extended to ± 2 days to allow for evaluation of ALT/AST.

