3.3.1. Toxicity Criteria

Table 7. Toxicity Criteria

Parameter	Definition ¹
Serious adverse event	Serious adverse event;
Increased liver transaminases ²	Serum AST ³ and/or ALT ⁴ are both increased to $>5 \times \text{ULN}^5$ (CTCAE ⁶ Grade ≥ 3);
Increased direct bilirubin ² (in absence of ALT/AST elevations)	Adapted from CTCAE ⁶ Grade ≥ 2 ;
Hypoglycemia	One (1) subject experiences ≥ 2 hypoglycemic events of <40 mg/dL (CTCAE ⁶ Grade ≥ 3) which do not meet SAE criteria;
Pancreatitis	Severe pain, vomiting; medical intervention indicated (CTCAE ⁶ Grade ≥ 3);
Decreased platelet count ²	Thrombocytopenia to $<100,000/\mu\text{L}$ [$<100 \times 10^9/\text{L}$];
Hypertriglyceridemia ²	>1000 mg/dL (CTCAE ⁶ Grade ≥ 4);
Increased serum creatinine ²	Serum creatinine to $2.2 \times \text{ULN}^5$ (CTCAE ⁶ Grade ≥ 3);
Diarrhea, enteritis or nausea	Increase of >6 stools/day over baseline; incontinence; hospitalization indicated; inadequate oral caloric or fluid intake (CTCAE ⁶ Grade ≥ 3);
ECG changes from baseline	Clinically significant ECG change from baseline including but not limited to interval changes (eg, PR, QTcF), ST-T wave changes, appearance of Q waves, atrial or ventricular rhythm abnormality, QRS axis deviation or ventricular conduction defect associated with clinical symptoms;
Prolongation of QT _c F interval ^{2,7}	QT _c F >500 msec (ie, CTCAE ⁶ Grade ≥ 3) or increase from baseline of ≥ 60 msec;
Unspecified	If considered appropriate by the medical monitor and investigator.

1. Unless considered to be unrelated to study medication by Investigator and Sponsor.
 2. To be confirmed by a repeat test.
 3. AST = aspartate aminotransferase.
 4. ALT = alanine aminotransferase.
 5. ULN = upper limit of normal reference range of the clinical laboratory.
 6. CTCAE = Common Terminology Criteria for Adverse Events.
 7. QT_cF = QT interval (Fridericia's correction).

In the event that a subject develops any of the toxicities outlined in Table 7, the subject will be followed until resolution and/or referred to an appropriate specialist

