5.2. Breaking the Blind

At the initiation of the study, the study site will be instructed on the method for breaking the blind. The method will be either a manual or electronic process. Blinding codes should only be broken in emergency situations for reasons of subject safety. Whenever possible, the investigator or sub-investigator should consult with a member of the study team prior to breaking the blind. When the blinding code is broken, the reason must be fully documented and entered on the case report form (CRF)/data collection tool (DCT).

Only the investigator site(s) and the study monitor(s) will be blinded to study treatment. Pfizer personnel will be unblinded to subject treatments in order to permit real-time interpretation of the safety and pharmacokinetic data; and provide information necessary to potentially alter the dose escalation sequence. The study monitor will remain blinded to treatment until all monitoring for the study has been completed. To minimize the potential for bias, treatment randomization information will be kept confidential by Pfizer personnel and will not be released to the investigator or investigator site personnel until the study database has been locked.

Blood specimens will be obtained from all subjects for pharmacokinetic analysis to maintain the study blind at the investigator site. Specimens from subjects randomized to placebo will not be routinely analyzed.

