9.8. Data Monitoring Committee

This study will not use a Data Monitoring Committee (E-DMC) or Internal Review Committee.

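### Meeting the MAD two-subject toxicity criterion ends escalation only; no rule requires a review before the Day 29 or Day 57 doses still due at that dose level

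*Protocol*

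**What the plan says.** Protocol Section 3.3 has a part headed "Multiple Ascending Dose Portion (n= 8 PF-06293620 drug :2 PBO"). It introduces its criteria with "Dose escalation will be terminated based on the following criteria". The first criterion is: "Two (2) or more subjects receiving PF-06293620 drug (but not placebo subjects) develop similar clinically significant laboratory, ECG or vital signs abnormalities", or severe adverse events in the same organ class, indicating dose-limiting toxicity. The sentence points to Table 3 for the toxicities, but they are listed in Table 7. One subject with two or more Grade 3 or higher hypoglycemic events that are not SAEs also meets it.

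The same section has a Dose Interruption part, which opens its mandatory rule with "Dosing will be interrupted in individual subjects when the following occurs". It covers confirmed ALT or AST above 5 times ULN. At 3 to 5 times ULN and rising, it requires a review of that subject before the next dose, and interruption is optional. On resumption it says "Missed doses will not be made up", and visits continue. For any Table 7 toxicity, Section 3.3.1 says "the subject will be followed until resolution and/or referred to an appropriate specialist".

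MAD doses are due on Days 1, 29 and 57 (Section 3.1). The visit procedures for Days 29 and 57 (Sections 6.3.13 and 6.3.16) list study drug administration without reference to the criterion. On who can see the count, Section 5.2 says "Only the investigator site(s) and the study monitor(s) will be blinded to study treatment", and Section 9.8 says "This study will not use a Data Monitoring Committee (E-DMC) or Internal Review Committee". The SAP adds no dosing rule. Its Section 3 gives the final MAD groups as 50 mg (8 active), 75 mg (16 active) and 150 mg (8 active).

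**The concern.** In the single-dose part, ending escalation deals with most of the risk, because each subject is dosed once. In the MAD part each subject has two more doses after Day 1. If two active subjects develop the same dose-limiting toxicity after dose 1 or dose 2, whether the others at that dose level get their next dose is left to discretion.

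The count is of active subjects only, so blinded sites cannot tell when it is reached. Only the unblinded sponsor team can, and nothing written obliges it to pause dosing while it looks. The preliminary data in Section 1.3.2 give a half-life of 9 to 18 days and a peak at about 4 to 10 days after a subcutaneous dose. A dose therefore cannot be withdrawn once given, and the decision before the dose is the point of control.

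**Working it through.** **1. Consequence attached to each rule (Protocol)**

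| Rule | Applies to | Tied to the next dose? |
|---|---|---|
| Two-subject criterion, 3.3 | Escalation | No |
| ALT/AST review and interruption, 3.3 | One subject | Yes, ALT/AST only |
| Follow-up or referral, 3.3.1 | One subject | No |
| Review after 80% of a cohort has 14 days of follow-up, 3.3 | Move to a higher dose | No |
| Withdrawal for safety, 6.4 | One subject, discretionary | Not by the criterion |
| Study termination, 14 | Whole study, discretionary | Not by the criterion |

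**2. Doses at stake (upper limits)**
- Cohort of 8 active and 2 placebo: before any Day 29 dose, 8 × 2 = 16 active (10 × 2 = 20 in all); before any Day 57 dose, 8 active (10 in all).
- 75 mg level, 16 active: 16 × 2 = 32 active doses, or 16 before Day 57.

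**3. The plan's own figure.** Table 10 gives P(X ≥ 2) = 1 − (1−p)^n − np(1−p)^(n−1). For n = 8 and p = 0.10, 0.15, 0.20, 0.25, 0.30, 0.33, 0.40 this is 0.187, 0.343, 0.497, 0.633, 0.745, 0.799, 0.894. The printed column (0.19, 0.34, 0.50, 0.63, 0.74, 0.80, 0.89) is reproduced within 0.01.

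**4. How often the criterion would be met.** The per-subject risks p are assumptions. Table 7 has ten rows besides hypoglycemia and the unspecified row. If these were independent with equal risk, P(any row) = 1 − (1 − P(X ≥ 2))^10.

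| p | One toxicity, n = 8 | Ten rows, n = 8 | One toxicity, n = 16 |
|---|---|---|---|
| 0.01 | 0.003 | 0.03 | 0.011 |
| 0.02 | 0.010 | 0.10 | 0.040 |
| 0.05 | 0.057 | 0.45 | 0.189 |

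The rows overlap, and only events before Day 57 can hold a dose, so the ten-row column is an illustration.

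**5. Unit of counting.** The criterion does not say whether its two subjects must be in the same cohort. At 75 mg and p = 0.05, P(at least 2 of 16) = 0.19. If the 16 are treated as two cohorts of 8, P(at least one cohort reaches two) = 1 − (1 − 0.0572)² = 0.11. Counting by cohort would miss one case in each half.

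**6. PK cost of a missed Day 29 dose.** Assume linear superposition with carry-over r per interval. After three doses Rac = 1 + r + r²; with Day 29 missed it is 1 + r².
- 75 mg, predicted Rac 1.14 (Section 1.3.3): r = 0.124, missed 1.016, so 11% low.
- 150 mg, predicted 1.4: r = 0.306, missed 1.094, so 22% low.
- Cross-check from a half-life of 9 to 18 days and a 28-day interval: r = 0.116 to 0.340, Rac 1.13 to 1.46, missed 1.01 to 1.12, so 10% to 23% low.

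**7. Time for a review.** Scheduled laboratory tests on Days 8 and 15 precede Day 29 by 21 and 14 days. Those on Days 36 (liver tests and CK only) and 43 precede Day 57 by 21 and 14 days.

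**8. Blinding.** If toxicity is unrelated to drug, two affected subjects in an 8:2 cohort are both active with probability (8/10)(7/9) = 0.62. A hold known to follow an active-only count would raise that to certainty for the site.

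**The case against.** The strongest reply is that this is a sponsor-open Phase 1 study that relies on joint judgement by design. The sponsor reads unblinded safety data in real time (Section 5.2). The 80% and 14-day review falls before Day 29 for later-enrolled subjects. Table 7 excludes events that the investigator and sponsor both consider unrelated to study medication, and most of its laboratory rows and QTcF need a confirming repeat test. SAEs reach the sponsor within 24 hours (Section 8.13.1) and suspected hypoglycemia as soon as possible (Section 7.6). Subjects can be withdrawn for safety, urgent safety measures are foreseen (Section 12.5) and the study can be stopped. MAD exposure may not exceed SAD exposure, and doses are four weeks apart. A sensible team would probably pause.

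Much of this stands. A reader might infer that subjects are unprotected or that the doses are unsafe; the documents support neither. A reader might also infer that the plan compels further dosing, because the Day 29 and Day 57 procedures list the dose without condition. It does not, since withdrawal and changes to dosing remain open. Nor is the criterion without effect where no higher dose is pending: Section 3.3 uses these rules to decide whether the maximum tolerated dose has been reached.

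What remains is narrower. None of these safeguards links the criterion to the next dose. The escalation review governs the move to a higher dose and does not cover findings after dose 2.

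A hold also has a blinding cost. Investigators rate causality (Section 8.8), and causal relationship is part of a primary endpoint (Section 2.2.1). That bears on how the hold is announced.

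**Conclusion.** The point holds as an incomplete safety rule. The plan defines a dose-limiting threshold for a repeat-dose part and does not say what happens to the doses still due when it is met. At the 50 mg and expanded 75 mg groups, both below the 150 mg already studied, the criterion informs the maximum tolerated dose but stops no dosing. Up to 16 active doses are affected per cohort of 8 active subjects, and up to 32 at 75 mg.

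A reader might conclude that a hold would always be rare. That is true for one uncommon toxicity (0.003 to 0.057 at 1% to 5% risk in 8 subjects) but not in general: across ten independent rows at those risks it is about 0.03 to 0.45. These figures rest on assumed risks and on independence. The PK figures rest on linear superposition, while the protocol reports exposure rising slightly more than in proportion to dose.

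This should be corrected for any MAD dosing still due. The SAP already lists final groups, so if dosing is complete the practical value is limited.

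**What to change.** Leave the toxicity definitions and the two-subject threshold as they are, and add to Section 3.3 (MAD):

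- When the existing criterion is met, counted across all active subjects at that dose level, the unblinded sponsor team starts a hold on further doses at that level. The hold lasts until the sponsor and investigators complete a documented safety review.
- The hold is announced to sites without disclosing treatment or the active-only count.
- A subject who meets the hypoglycemia criterion has only his or her own next dose held, pending the same review.
- The ±2 day dosing window and the existing missed-dose rule apply.

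The SAP should state that Day 57 AUCtau and Rac are reported separately or excluded for subjects with a missed dose.

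The cost is a few sentences in an amendment, using existing reviewers and data, plus an occasional delayed or missed dose. The ±2 day window was written for one subject's ALT/AST and may be too short for a level-wide review, especially with staggered enrolment or a finding just before dosing. A missed Day 29 dose makes Rac about 11% to 22% low, and a missed Day 57 dose removes Day 57 AUCtau and Rac for that subject. Some unblinding risk remains, because a site may guess why a hold was called. Keeping the hypoglycemia hold individual avoids whole-cohort holds that would otherwise occur with probability 1 − (1−p)^8 = 0.08 to 0.34 at assumed p = 0.01 to 0.05.
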